7.4 Handling of Missing, Unused, and Spurious Data and Dropouts

The primary analysis will be based on all evaluable data. Handling of dropouts and missing data will depend on their frequency and the nature of the outcome measure.

For those subjects who do not complete a follow-up call, the analysis will include all data up to the last collected point or follow-up call. Subjects who completed the procedure phase will not be replaced. If the subject discontinues prior to randomization or during the procedure phase, she/he will be replaced, but will count toward the total sample size if they were randomized.

7.5 Adjustments for Multiple Comparisons

No multiplicity adjustments will be considered in this study. As aforementioned, poolability of data from stage 1 and 2 will be tested and justified. Dose-response relationship will be evaluated for each of the study regimens. Between-group comparisons will be summarized with point estimates and 95% confidence intervals. P-values will be provided for reference purpose only.

7.6 Demographic and Other Baseline Characteristics

Subject demographics, medical history will be summarized using descriptive statistics for continuous variables (N, mean, standard deviation, number of observations, minimum and maximum) and frequency tables for discrete variables.

Baseline demographic data will be summarized and reported in a table entitled Summary of Subject Demographics. This table summarizes the subject population with respect to age at entry into the study, gender. Age will be reported in years, and will be summarized using descriptive statistics: N, arithmetic mean, standard deviation, median, and range (i.e., minimum and maximum values). Subjects with missing data that cannot be resolved prior to database lock will not be included in the tabulation and excluded from the summary statistics; Gender will be summarized using counts and percentages. In addition to the reported values, unknown or unreported values will also be reported. The supportive data for the demographics table will be presented in a listing entitled Subject Demographics.

7.7 Interim Review

The interim review will be performed at the end of stage 1 when all subjects have completed the evaluation. BIS™ values will be estimated using logistic regression (Hill equation) based on primary outcome “Responsive: Yes/No”. One or more regimens may be dropped upon interim results for safety concern (unacceptable safety events per clinical judgment).

7.8 Evaluation of Objectives

The objective of this study is to investigate the relationship between BIS™ and anesthetic agents across a wide range of hypnotic states and to provide evidence to support BIS™ performance in use with these anesthetic agents.

Primary Objective:

To determine BIS₅₀ (BIS™ value at which 50% of subjects will be unresponsive at given drug concentrations).

Secondary Objective:

To determine BIS₉₅ (BIS™ value at which 95% of subjects will be unresponsive at given drug concentrations).

The logistic model (simplified Emax model) will be used to estimate the BIS™ values, along with corresponding 95% confidence intervals and standard errors.

Prediction Probability score (P_k) will be calculated following the details in the Smith's paper (Smith 1996). All technical details were provided in the Appendix in the paper. SAS procedure PROC LOGISTIC will be used to perform the calculation.

Differences in subject characteristics will be analyzed using t-test (continuous variables including age, weight and height) or Chi-square test (categorical variables including gender). The correlation coefficient for the relationship between sedation score and BIS™ value will be calculated for each group using a linear regression model. Additionally, BIS™ values and haemodynamic variables will be analyzed within the groups using analysis of variance (ANOVA) for repeated measures.

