The opioids (remifentanil or fentanyl) will be administered via the target-controlled infusion (TCI) pump using either the preprogrammed pump protocols or computer-controlled program, e.g., TIVA Trainer, or another computer-controlled program, to ensure that the targeted effect-site concentration of a drug is reached and maintained at each drug concentration plateau. 1% propofol and remifentanil or fentanyl diluted to a single concentration of 50 µg/ml will be used in this study. The infusion rate between 0 and 1200 ml/hr will be used to achieve a targeted concentration of remifentanil and fentanyl. For remifentanil, Minto [1, 46] PK/PD model will be used. The kinetic model for fentanyl will not be weight-adjusted [2]. Phenylephrine may be provided at a concentration of 100 mcg/mL and lidocaine can be administered per Investigator discretion as a bolus over 3-5 seconds at a maximum concentration of 100mg. Antiemetic / anti-nausea medication (i.e. Ondansetron) may be used prophylactically on all subjects at the investigator's discretion.

Inhalation anesthetic drugs will be administered via a tight-fitting face mask or a laryngeal mask (LMA). Subjects will be connected to a circular breathing system of an anesthesia machine. After the subject loses responsiveness, a laryngeal mask airway (LMA) may be inserted as needed to facilitate airway control at

deeper levels of anesthesia. Inhalation agents will be administered with O₂ to maintain saturation of greater than 90%.

Sensor Application

The BIS™ sensor will be applied per its IFU. Subjects will have an intravenous catheter inserted for fluid and drug administration. The TES sensor will be applied per its IFU. A stimulation of 2-5mA, 5 Hz for 1-5 seconds or per IFU will be provided to ensure proper application

The subject will rest for at least 12 minutes before starting any regimen.

MOAA/S, Picture Recall Test and Tetanic Electrical Stimulation (TES)

At each steady-state step and after equilibration, the MOAA/S assessment will be administered by an anesthesiologist. The same anesthesiologist, trained and delegated to perform the MOAA/S assessment on the Delegation of Tasks Log must perform all MOAA/S assessments for a specific subject, refer to **Appendix A**. The maximum number of delegated Anesthesiologists per site to perform the MOAA/S assessment is two in order to ensure consistency across physicians.

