assessment. Then, TES will be initiated following the Instructions for Use (IFU) for the XAVANT STIMPOD™ NMS 410/450X device. TES will then be initiated once the subject reaches a MOAA/S 0, BIS™ value <40 at the highest concentration of anesthesia anticipated. Stimulation will start at 20mA, 50 Hz delivered for 1-5 seconds. If the subject does not purposefully (i.e. attempting to push the stimulus away) respond, the stimulation will increase to 30mA, 50Hz for 1-5 seconds, then 40mA, 50Hz for 1-5 seconds and finally to 50mA, 50Hz for 1-5 seconds. If there is still no purposeful response, the subject will be considered a non-purposeful responder (i.e. exhibiting a reflex withdrawal, facial grimace, or groan) and their response such as withdrawal of extremity, facial grimace or other will be recorded along with the BIS™ value prior to stimulation, at the end of all assessments and approximately 2 minutes following all assessments. If the subject does respond to any of the stimulations with a purposeful response, the TES will be ended, the response will be noted and the BIS™ value will be recorded at the time TES is ended at approximately 2 minutes following the stimulation. Anesthesia will then be decreased in the same steps until subject is conscious.

Sevoflurane Group

After approximately 2 minutes of baseline measurement, sevoflurane will be administered in steps to achieve a loss of consciousness via a tight-face mask by increasing the end-tidal concentration of Sevoflurane (ET_{SEVO}). Targeted concentration for ET_{SEVO} are 0.2, 0.5, 0.7, 1, 2, 3, 4, 5% or higher until a BIS™ value not less than 30 is reached or per Investigator's discretion. The BIS™ value should be taken to at least 40, but not intentionally below 30.. The equilibration time for each targeted concentration will be approximately 12 minutes to maintain a constant ET_{SEVO}.

The BIS™ value, MOAA/S score and picture recall test will be assessed when the patient is awake and prior to the induction of anesthetic and at the different ET_{SEVO} concentrations. TES will then be initiated once the subject reaches a MOAA/S =0 and the BIS™ value <40 at the highest concentration of anesthesia anticipated. The BIS™ value will be recorded at the time of subject's response and approximately 2 minutes following the TES assessment.

ET_{SEVO} is decreased by the same steps until consciousness is regained.

Sevoflurane with Remifentanil Group

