The Evaluation of BIS™ and Levels of Sedation in Health Volunteers (OLIVER) Study is a multi-center, prospective randomized study to collect data to evaluate the relationship between BIS™ and inhaled anesthetics without and with opioids. Healthy Volunteers will be sequentially assigned to one of the study groups of anesthetics regimens at each clinical site. The BIS™ bilateral sensor will be placed on the subject's forehead to study the effects of these drugs on the brain. Each volunteer will be given a dose range of sequences of the target drug to achieve targeted drug concentration. Five groups of anesthetics regimens will be studied as follows:

1. Sevoflurane alone
2. Sevoflurane with Remifentanil
3. Sevoflurane with Fentanyl
4. Desflurane alone
5. Isoflurane alone

At each steady-state step, and after at least 12 minutes to achieve equilibrium, the Modified Observer's Assessment of Alertness/Sedation (MOAA/S) scale will be used to perform sedation/loss of consciousness assessment. The loss of verbal response will be defined according to the MOAA/S score value < 2 (0-1) and the presence of verbal response at values ≥ 2 (2-5).

The expected duration of each subject's participation is approximately 6 hours for both enrollment and procedure. The Enrollment Visit should take approximately 2 hours to complete, and the Study Visit will be approximately 4 hours per subject. Each subject will be contacted by phone within 48 hours of the study participation. Subjects will be continuously monitored throughout the study.

This document provides a detailed description of the statistical methods and procedures to be implemented during the analysis of the study.

This statistical analysis plan (SAP) is based on Version 5.0 of the Protocol dated on 06-JAN-2022.

4 Study Objectives

4.1 Primary Objective:

To determine BIS₅₀ (BIS™ value at which 50% of subjects will be unresponsive at a given drug concentration).

4.2 Secondary Objective:

To determine BIS₉₅ (BIS™ value at which 95% of subjects will be unresponsive at a given drug concentration).

[BIS] Statistical Analysis Plan

Revision [\[x\]](#)

Page 6 of 20

Form

Medtronic

To determine Prediction Probability score (P_k) for correctly predicting if the subject was responsive or unresponsive.

5 Investigation Plan

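### Three supportive analyses in SAP 7.8 do not fit the design: a t-test for five regimens, a linear correlation with no subject term, and repeated-measures ANOVA on a ladder of unequal length

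*SAP*

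**What the plan says.** The last paragraph of SAP 7.8 (Evaluation of Objectives) lists three analyses beyond BIS50, BIS95 and Pk.

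- Baseline: "Differences in subject characteristics will be analyzed using t-test" for continuous variables (age, weight, height), with a Chi-square test for categorical ones such as gender. No pairs and no reference group are given. SAP section 3 states: "Five groups of anesthetics regimens will be studied as follows".
- Sedation score against BIS: "The correlation coefficient for the relationship between sedation score and BIS™ value will be calculated for each group using a linear regression model". No subject term, rank method or interval is mentioned.
- BIS and haemodynamics over the procedure: "BIS™ values and haemodynamic variables will be analyzed within the groups using analysis of variance (ANOVA) for repeated measures". The repeated factor, the covariance structure and the treatment of absent steps are not stated.

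The design facts come from the protocol. Appendix A gives MOAA/S as six ordered categories, 0 to 5. Section 10.5 has it scored repeatedly in each subject: "At each steady-state step and after equilibration, the MOAA/S assessment will be administered by an anesthesiologist". In the sevoflurane group, also in section 10.5, concentration rises through eight listed levels or higher "until a BIS™ value not less than 30 is reached or per Investigator's discretion", then falls through the same levels until the subject is conscious again. The safety text in 10.5 also lets the principal investigator alter steps.

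SAP 7.5 makes no multiplicity adjustment and treats p-values as informational. SAP 7.4 names no missing-data method. It leaves the choice to how often data are missing and to the type of outcome.

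**The concern.** Each method assumes a data structure that this trial does not produce. A t-test assumes two groups. An ordinary linear regression assumes independent records and a numeric score. Classical repeated-measures ANOVA assumes that every subject is observed at every level of the repeated factor.

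Two things are at stake. The first is reproducibility: two programmers working from SAP 7.8 could produce different baseline tables and different ANOVA data sets, both consistent with the text. The second is interpretation. A chance baseline difference may attract comment, a correlation may carry an interval with the wrong width, and a BIS or haemodynamic profile may describe a selected subset of the group. The third is the most substantive, because it would affect estimates as well as p-values.

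**Working it through.** **The plan's own figure.** SAP 7.8 gives no number for these analyses. The nearest is N = 24 per regimen in SAP section 6. Inputs: difference 0.15, SD 0.25, two-sided alpha 0.05, power 80%. Then d = 0.15/0.25 = 0.6, and a one-sample t-test with noncentrality 0.6 × √24 = 2.94 has power 0.804. The figure reproduces, and nothing below changes it.

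**1. Baseline t-test.** Five regimens give 5 × 4/2 = 10 pairs. If the contrasts were independent, the chance of at least one p < 0.05 under no difference would be 1 − 0.95^10 = 40%. They are not independent, because each group enters four pairs, so it was simulated (20,000 runs, normal data, equal means):

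| Subjects per group | Any of 10 pairwise t-tests p < 0.05 | One five-group F-test p < 0.05 |
|---|---|---|
| 30 (planned maximum) | 28.1% | 4.9% |
| 10 (stage 1) | 28.8% | 5.1% |

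These are chances per variable. They apply only if all ten pairs are tested.

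**2. Correlation of MOAA/S with BIS.** In a simple linear regression, the test of the slope and the test of the correlation are the same, so slope-interval coverage was used to judge the precision that the default output would report. The documents give no within-subject correlation, so a range was assumed: 30 subjects, 8 to 17 records each, scores running from 5 to 0 and back to 5, a true slope of 8 BIS points per score level, and subject intercept plus residual SD of 10 in total. The share of that variance due to subject (ICC) was set at 0.1, 0.3 and 0.5. In the varying-slope case the between-subject slope SD was 10 × √ICC/2.5, that is 1.26, 2.19 and 2.83. Coverage of the nominal 95% interval over 1,500 runs:

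| ICC (assumed) | Subjects differ in level only | Subjects differ in level and slope |
|---|---|---|
| 0.1 | 96% | 90% |
| 0.3 | 98% | 83% |
| 0.5 | 99% | 76% |

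Ignoring the subject therefore makes the interval too wide in one case and too narrow in the other. The direction cannot be settled before the data are seen.

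**3. Repeated-measures ANOVA.** No arithmetic is possible, so the passages are set side by side.

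- Going up, a subject's last step is set by that subject's BIS or by investigator discretion. A subject stopped early has no record at the higher concentrations.
- Coming down, the last step is set by return of consciousness. A subject who wakes early has no record at the lowest concentrations.
- Steps may also be changed for safety.

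The layout is therefore unbalanced by design, and BIS is both a stopping variable and one of the analysed outcomes. A classical ANOVA on complete rows keeps only subjects observed at every included level. On the way up, those are subjects taken to the top of the range; on the way down, those who did not wake early. The documents do not say how many subjects will reach any given step, so the loss cannot be computed.

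**The case against.** The strongest defence is that nothing depends on these analyses. The objectives are BIS50, BIS95 and Pk. SAP 7.5 makes p-values informational, and SAP 7.6 already plans descriptive baseline summaries. The sponsor may intend pairwise t-tests, a purely descriptive correlation, or a likelihood-based repeated-measures model. Most of this stands, and it is why the point is small. It does not supply the missing specification, and the status of p-values does not protect the BIS and haemodynamic profiles from selection.

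Four stronger readings are tempting, and the documents do not support them.

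- A reader might infer that the baseline p-values are themselves inflated. They are not: each two-group p-value is valid, and what rises is the chance that at least one of ten is small. Compounding this over age, weight and height as if independent is also unsound, since weight and height are related.
- A reader might infer that the correlation's standard error is too small. SAP 7.8 plans no standard error for it, and the check shows error in both directions.
- A reader might infer that the ANOVA is biased toward resistant subjects. Complete-row fitting is a common default, not a rule in the SAP, and discretion and safety also decide who reaches the top step.
- A reader might try to count the subjects lost. Any such number would be an assumed fraction multiplied by 30.

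Using a linear correlation on a six-level score is in part a matter of preference. The absence of a subject term is not.

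**Conclusion.** The point holds as a minor one. SAP 7.8 names three supportive analyses that do not match five regimens, repeated ordinal scores and a ladder whose length varies with the subject.

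- **Baseline:** about 28% against 5% per variable, conditional on all ten pairs being tested without adjustment.
- **Correlation:** any interval or p-value is unreliable, with coverage between 76% and 99% under the assumed ICC and slope variation. The coefficient can still be read as a description.
- **ANOVA:** an unbalanced layout follows from the stopping rules. Selective loss of subjects follows only if the model is fitted on complete rows, and its size is unknown.

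BIS50, BIS95, Pk and the sample size of 24 do not depend on any of the three.

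**What to change.** Revise the last paragraph of SAP 7.8.

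1. **Baseline.** Either describe the five groups without tests, or use one five-group comparison per continuous variable (one-way ANOVA or Kruskal-Wallis) and keep the Chi-square test for sex.
2. **MOAA/S and BIS.** Within each regimen, use a rank-based or ordinal-model association, with the interval from a bootstrap that resamples subjects rather than records.
3. **BIS and haemodynamics.** Use a likelihood-based linear mixed model on all observed steps, with step or concentration, ascending or descending limb, and a subject random effect, and state the covariance structure. State that stopping depends on BIS. With BIS as the outcome, using all recorded values makes the model much more defensible than complete rows, provided that stopping is driven by those values. For haemodynamic outcomes the stopping variable is a different one, so include BIS in the model or label the result descriptive.

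The cost is SAP wording and standard SAS procedures. No new data, visits or subjects are needed.

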7.9 Safety Evaluation

Safety evaluation will be based on all enrolled subjects in this study. Adverse events will be summarized using frequency counts and percentages. Descriptive statistics will be provided by event type, severity, and relationship to study procedures and devices.

Unanticipated device effect (UADE), Serious Adverse Device Effect (SADE) and Unanticipated Serious Adverse Device Effect (USADE) will also be summarized by frequency table. Individual listings of adverse

events, including event type, start date, duration, severity, and device-relatedness, will be provided as appropriate.

7.10 Health Outcomes Analyses

This section is not applicable to this study.

7.11 Changes to Planned Analysis

This section is not applicable to this study.

8 Validation Requirements

Output will be validated by level I or II validation.

Level I: The peer reviewer independently programs output and then compares the output with that generated by the original Statistical Programmer.

Level II: The peer reviewer reviews the code; where appropriate, performs manual calculations or simple programming checks to verify the output.

9 Statistical Appendices

I. Bayesian Data Integration with Power Prior

A. Power Prior

Consider statistical data integration of two sources: historical data and current data. Simply pooling the data may not yield valid scientific inferences due to potential variations across data sources. The variations may or may not be observed and ignoring the variations will likely lead to biased estimates. For valid inferences, appropriate statistical methods and justifications will be needed. The Bayesian power prior is a statistical method often used to achieve the data integration. The detailed formulation is as follows.

Let the data for the current study be denoted by D and the corresponding likelihood function be denoted as $L(\theta|D)$, where θ is a vector of parameters of interest. Suppose we have the historical data D_0 from a previous study. Let $L(\theta|D_0)$ denote the likelihood function for the historical data D_0 . Here, $L(\theta|D)$ and $L(\theta|D_0)$ are general likelihood functions for the corresponding statistical model to be used for inferences.

The basic formulation of the power prior can be written as:

$$\pi(\theta|D_0, \alpha_0) \propto L(\theta|D_0)^{\alpha_0} \pi_0(\theta),$$

where $0 \leq \alpha_0 \leq 1$ is a *scalar* parameter and $\pi_0(\theta)$ is the *initial prior* for the parameter θ before the historical data D_0 is observed. In many applications, $\pi_0(\theta)$ is taken to be an improper prior. With the power prior, the corresponding posterior distribution of θ is given by

$$\pi(\theta|D, D_0, \alpha_0) \propto L(\theta|D) L(\theta|D_0)^{\alpha_0} \pi_0(\theta).$$

From the above formula, we see that α_0 weights the historical data relative to the likelihood of the current data, and thus the parameter α_0 controls the influence of the historical data on $L(\theta|D)$. The parameter α_0 can be interpreted as a precision parameter for the historical data. Since D_0 is historical data, it is unnatural in practical applications to weight the historical data more than the current data; thus it is scientifically sound to restrict the range of α_0 to be between 0 and 1, that is, $0 \leq \alpha_0 \leq 1$. Setting $\alpha_0 = 1$ corresponds to the update of $\pi_0(\theta)$ using the Bayes theorem. That is, with $\alpha_0 = 1$ corresponds to the posterior distribution of θ based on the historical data D_0 . When $\alpha_0 = 0$, the prior does not depend on the historical data; in this case, $\pi(\theta|D_0, \alpha_0 = 0) = \pi_0(\theta)$. Thus, $\alpha_0 = 0$ is equivalent to a prior specification without incorporation of historical data. Therefore, the approach can be viewed as a generalization of the usual Bayesian update of $\pi_0(\theta)$. The parameter α_0 allows to control the influence of the historical data on the current study. Such control is important in cases where there is heterogeneity between the previous and current studies.

Since the power prior is essentially a likelihood function raised to a power, it shares all the properties that likelihood functions have, and therefore has several advantages over other non-likelihood-based priors. Due to its validity and ease of interpretation, the power prior approach has been widely adopted in practical applications and is commonly seen in medical device regulatory submissions.

[BIS] Statistical Analysis Plan

Revision [\[x\]](#)

Page 15 of 20

Form

Medtronic

B. Primary Efficacy Endpoint

In this study, the primary efficacy endpoint is the BIS₅₀, defined as the BIS™ value at which 50% of subjects are unresponsive at given drug concentrations. The BIS™ is a variable derived from the electroencephalograph (EEG) that has been reported to have the ability to measure the hypnotic component of the anesthetic state. It is a dimensionless number from 0 to 100, and decreasing values indicate more sedation and hypnosis. The MOAA/S scales and BIS™ value will be assessed and recorded when the subject is awake and at different drug concentrations.

The dose-response relationship will be estimated using the logistic model. The model is written as follows:

$$P = \frac{e^{a+bX}}{1 + e^{a+bX}}$$

where P is the probability of “unresponsive”, X is the explanatory variable (BIS™ value or anesthetic agent concentration on the log scale), and a & b are corresponding model parameters.

In the context of the dose-response model, let θ represents the target BIS™ value on the log scale. Let $D = \{y_1\}$ and $D_0 = \{y_0\}$ represent the current data and prior data respectively. The parameter estimation will be carried out based on the posterior distribution (upon normalization):

$$\pi(\theta|D, D_0, \widehat{\alpha}_0) \propto L(\theta|D) L(\theta|D_0)^{\widehat{\alpha}_0} \pi_0(\theta)$$

where the notation $\widehat{\alpha}_0$ is used to denote that the estimate of α_0 based on the observed data. Of note that the estimate depends on the current data (D) and prior data (D_0). In conjunction with a pre-specified decision rule controlling the prior data weight, the estimate of $\widehat{\alpha}_0$ represents a measure of similarity between the current data and prior data. Alternatively, in the absence of $\widehat{\alpha}_0$, i.e., full weight would be given to the prior data.

C. Statistical Analysis

The Bayesian power prior with discounting function will be used to estimate the target parameter and determine $\widehat{\alpha}_0$, the strength of the prior data used to support the current data. Of note $\widehat{\alpha}_0$ ranges from 0 to 1, where 1 means that 100% of the prior data is used and 0 means that no prior data is used. Before beginning the current study, an initial value is chosen for $\widehat{\alpha}_0$, and let's call this value α_{max} . This α_{max} value is the maximum strength that the prior data can receive. For this study, we intend to use the same protocol and enrollment criteria for the prior and current studies, and therefore believe that a value of $\alpha_{max} = 1$ is appropriate.

The study data will be analyzed using the power prior method along with discounting function. The method will discount α_{max} to an appropriate value $\widehat{\alpha}_0$ where $\widehat{\alpha}_0 \leq \alpha_{max}$. This discounting scale is based on the discounting function which will be discussed in detail in the next section.

Under the adaptive procedure, if the current study data diverges from the prior data, the discounting function will discount the strength of the prior data. Alternatively, if the prior and current study data agree, there will be no or minimal penalty from the discounting function, thus a large amount of data information would be integrated into current data for statistical inferences.

The primary analysis set consists of all evaluable subjects and will be used for the primary analysis. The per-protocol set will be used for supportive analysis.

D. Discounting Function Estimation Method

The method of power prior discounting function is comprised of four steps: **Compare, Discount, Combine, and Estimate**. Details in each step are presented below.

Compare:

We start by stochastically comparing current data vs prior data as follows.

For each study group, we separately fit the model to the combined prior and current data:

$$H(p_i) = \beta_0 + \beta_1 I(i \in \text{prior}) + \beta_2 d_i + \varepsilon_i, \quad \varepsilon_i \sim N(0, \sigma^2),$$

where H is the inverse logit function, p_i is the probability of target response, d_i is the dose concentration (log scale), and the indication function $I(i \in \text{prior}) = 1$ if the subject is from the prior data, and 0 otherwise. With a flat prior on each parameter, we estimate the posterior probability that $\beta_1 > 0$ by first computing the parameter, using Monte Carlo sampling

$$p^* = P[\beta_1 > 0 \mid D, D_0].$$

Having calculated the parameter for each group, we use the transformation:

$$p = \begin{cases} 2p^*, & p^* \leq 0.5 \\ 2(1 - p^*), & p^* > 0.5 \end{cases}$$

Now, under this transformation, if p is close to 0, there is a high probability that the current data and prior data come from different populations and discounting should be applied to reduce the influence of the prior. On the other hand, if p is close to 1, there is a high probability that the current data and prior data are from similar populations and minimal discounting should be applied.

Discount:

[figure not shown]
Let discount α_{max} based on the value of p from the **Compare** step and the discounting function $F(p)$,

$$\widehat{\alpha_0} = \alpha_{max} F(p),$$

where $F(p)$ is a function between 0 and 1. A two-sided Weibull function will be utilized as follows:

$$F(p) = 1 - e^{-(p/\lambda)^k}.$$

For this study, we will be using a shape parameter of $k = 3$ and a scale parameter of $\lambda = 0.5$ (illustrated below).

